10.1.3. Additional Endpoints

- The percentage of target aneurysm ruptures up to 1 year, 3 years and 5 years. This endpoint will be evaluated by the independent core laboratory.
- No migration (defined as ≤ 2 mm) of the device at 1 year, 3 years and 5 years. This endpoint will be evaluated by the independent core laboratory.

10.1.4. Adverse Events and Clinical Complications

Adverse Events, SAEs, device- or procedure-related AEs, USADEs, UADEs, and deaths will be coded using the MedDRA system and summarized with frequencies.

Study device malfunctions will also be summarized.

In addition, a listing of adverse events will be provided for any subject that was consented and started the study procedure but did not undergo attempted treatment with the study device and therefore is not part of the modified Intent To Treat (mITT) population.

10.1.5. Levels of Significance

A 2-sided alpha of 0.05 will be used for statistical testing and confidence intervals unless otherwise noted. There will be no adjustment of significance levels or p-values for testing multiple hypotheses. Both primary endpoints must be met for study success and the secondary effectiveness endpoint of technical success will only be tested if the primary endpoints are met.

10.1.6. Analysis Datasets

Modified Intent to Treat Analysis Set

The mITT analysis set consists of all enrolled subjects in whom treatment with the PulseRider device is attempted as defined by advancement of any portion of the PulseRider device outside of the distal end of the microcatheter inside the subject. This includes subjects in which the PulseRider is not fully advanced outside of the microcatheter. It is possible that the PulseRider device may not reach the target aneurysm, and as a result the treating physician does not advance the device outside of the distal end of the microcatheter. In the rare event that this happens, the subject will not be considered part of the mITT population and will instead be followed for 30 days.

Per Protocol (PP) Analysis Set

The PP analysis set consists of all subjects who meet the following criteria:

- there are no major deviations from the protocol eligibility criteria or DAPT requirements
- the subject is successfully implanted with the PulseRider device

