1.3.2. PulseRider HDE Clinical Study

Pulsar Vascular Inc. sponsored a HDE clinical study to evaluate the safety and probable benefit of the PulseRider Aneurysm Neck Reconstruction Device under IDE G130268. The Adjunctive Neurovascular Support for Wide-Neck Aneurysm Embolization and Reconstruction Study (ANSWER) was a prospective, multi-center, non-randomized study designed to evaluate the safety of the PulseRider device in patients undergoing treatment for intracranial bifurcation aneurysms of the carotid terminus or basilar artery. Thirty-four subjects were enrolled in the clinical study at 10 clinical sites in the US.

The PulseRider is an adjunctive device to support the neck of the aneurysm and it is intended to be used with embolic coils. The device was placed at the neck of the intended target aneurysm and detached in 34/34 cases, a 100% success rate. The blinded core lab adjudicated Raymond I and II combined score was 87.9% at 180 days post-procedure. There were two secondary procedures performed during the course of the study. The HDE study was limited to basilar and carotid terminus aneurysms only and although the safety profile of the device is favorable and reported data is encouraging, a larger study in additional territories is desired.

A report of the full data set with six-month follow-up was submitted to the Food and Drug Administration (FDA) in June 2016. The HDE was approved on June 19, 2017 for use in bifurcation aneurysms in the carotid terminus and basilar arteries. Further detail on the ANSWER Study is located in the Investigator Brochure.

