The schedule of assessments is listed in Table 7.15A. The baseline imaging must be completed within 180 days of the index procedure. All baseline tests should be completed within 60 days prior to the device placement procedure. This 60 days is inclusive of the procedure day, prior to the index procedure. The NIHSS, mRS, pregnancy test (if required), and the imaging study confirming anatomic eligibility criteria are required on the day of the index procedure

Final eligibility cannot be determined until the immediate pre-procedure DSA is completed. This takes place immediately prior to the index procedure and it is expected that some subjects may be excluded at that time. Excluded subjects will undergo routine clinical care for their aneurysm treatment and will be considered a screen failure for the study.

A patient is considered enrolled in this study after the patient is consented, approval of imaging screening committee is received, pre-procedure angiogram is completed and the treating physician confirms the subject meets all eligibility criteria on the day of the study procedure.

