7.4. Procedure Assessments

Index procedure start/end times will be recorded and the following definitions apply to the index procedure:

- Procedure start time is defined as the point when the guiding catheter is introduced into the subject.
- Procedure end time is defined as the time the last catheter is removed from the subject.

Procedural assessments – pre-treatment, intra-treatment and post-treatment include:

- Procedural medications
- Event assessment
 - Adverse events
 - Protocol deviations
 - Device malfunctions/deficiency
 - Angiogram
 - Post-treatment aneurysm occlusion per Raymond– Roy scale
 - Send the pre-treatment, intra-procedure, and post-treatment DSA to the core lab

At a minimum, the following data will also be captured during the procedure:

- Name of the implanting physician
- Aneurysm and vessel dimensions
- PulseRider device implanted
- Device implant success
- Adjunctive devices used including coils and balloons
- Ancillary devices used including the microcatheter
- Fluoroscopy time

- Presence of vasospasm (vessel and times of onset/resolution). Vasospasm will be captured as an adverse event only if it leads to a subsequent thrombotic or ischemic event.

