10.1.2. Secondary Endpoints

- Technical Success is defined as successful implantation of device— physician able to access target aneurysm, deploy PulseRider device at the neck of aneurysm and device was detached successfully. This endpoint will be reported by the investigator. The following hypothesis test of this endpoint will be performed if the primary safety and effectiveness endpoint null hypotheses are both rejected:
 - Null hypothesis H_0 : $p_{\text{TechnicalSuccess}} \leq \text{PG of } 79\%$
 - Alternative hypothesis H_A : $p_{\text{TechnicalSuccess}} > \text{PG of } 79\%$
 - Where $p_{\text{TechnicalSuccess}}$ is the rate of technical success
 - Decision Criterion: The decision will be made to reject the null hypotheses and conclude the alternative hypothesis if the lower bound of a two-sided 95% normal approximation based confidence interval is $> \text{PG of } 79\%$. With 160 subjects, a rate for technical success of at least 85% is required to demonstrate success on this endpoint.
- Ability to retain embolic coils within aneurysm immediately post-procedure (as evaluated by the core lab)
- Complete aneurysm occlusion at 3 years and 5 years. Complete aneurysm occlusion is defined as Raymond I. Aneurysm occlusion grading will be evaluated by the independent core laboratory.
- Adequate aneurysm occlusion (defined as Raymond I and II combined) at 1 year, 3 years and at 5 years. Aneurysm occlusion grading will be evaluated by the independent core laboratory.
- The percentage of target aneurysms that are retreated through 1 year, 3 years and 5 years. Retreatment will be reported by the investigator.

- The percentage of subjects with significant stenosis defined as $> 50\%$ at implant site at 1 year, 3 years and 5 years. This endpoint will be evaluated by the independent core laboratory
- The percentage of subjects with mRS 0 – 2 at 1 year, 3 years and 5 years

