10.3.5. Secondary Endpoint Analyses

The analysis of technical success which is reported by the investigator will be conducted on the mITT analysis set. The endpoint will be considered successful if the lower bound of the 2-sided 95% normal approximation based confidence interval for the rate is greater than a performance goal of 79%.

The analyses of the remaining secondary effectiveness endpoints listed below will be conducted on the PP analysis set using the observed data.

- The ability to retain embolic coils within aneurysm immediately post-procedure as reported by the independent core laboratory
- Complete aneurysm occlusion at 3 years and 5 years as reported by the independent core laboratory
- Adequate aneurysm occlusion at 1 year, at 3 years and 5 years as reported by the independent core laboratory
- The percentage of target aneurysms that are retreated through the 1 year, 3 year and 5 year as reported by the investigator
- The percentage of subjects with significant stenosis defined as > 50% at implant site at 1 year, 3 years and 5 years as reported by the independent core laboratory
- The percentage of subjects with mRS 0-2 at 1 year, 3 years and 5 years

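### Technical success requires reaching the aneurysm, but it is tested on a set that drops enrolled subjects whose device never got there

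*Combined protocol and SAP*

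**What the plan says.** Section 10.1.2 (and 3.2.3) defines technical success by three elements: "physician able to access target aneurysm, deploy PulseRider device at the neck of aneurysm and device was detached successfully". Section 10.3.5 names the analysis set: "The analysis of technical success which is reported by the investigator will be conducted on the mITT analysis set". The test passes if the lower limit of the two-sided 95% normal-approximation interval exceeds 79%, and it is carried out only if both primary endpoints are met. Section 10.1.2 adds: "With 160 subjects, a rate for technical success of at least 85% is required to demonstrate success on this endpoint".

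Section 10.1.6 admits an enrolled subject to mITT once any part of the device has passed the distal end of the microcatheter. Partial advancement is enough: "This includes subjects in which the PulseRider is not fully advanced outside of the microcatheter". It then considers a device that does not reach the aneurysm and is therefore kept inside the microcatheter. Of that case it says: "the subject will not be considered part of the mITT population and will instead be followed for 30 days". It calls this rare and gives no rate.

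Enrolment comes before this point. Section 7.2.1 says: "A patient is considered enrolled in this study after the patient is consented, approval of imaging screening committee is received, pre-procedure angiogram is completed", together with the physician's confirmation of eligibility on the procedure day.

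**The concern.** The first thing the endpoint measures is whether the physician could get to the aneurysm. The analysis set then removes one kind of subject for whom the answer was no. Membership of the denominator therefore depends on the outcome, and every subject lost this way would have counted as a failure.

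These subjects are not screen failures. They were enrolled after the procedure-day angiogram, after the physician had judged placement technically feasible (inclusion criterion 5), and after anatomy prohibiting safe access had been excluded (exclusion criterion 17). Failure to deliver the device after those checks is what a technical success rate should show.

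At stake are the stated success rate and, near the threshold, the result of the only tested secondary endpoint, in a study meant to support a premarket approval application (section 2.1).

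**Working it through.** **1. Does any other section restore these subjects?**
- Section 10.1.4 provides a listing of their adverse events.
- Section 10.3.2 provides disposition counts.
- Section 10.3.9 plans no imputation for the secondary endpoint.
- Section 10.3.10 covers the primary endpoints only.

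None returns them to the technical success denominator. Subjects whose device left the microcatheter but was not implanted do stay in mITT and count as failures, so the gap is confined to devices that never left it.

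**2. The plan's own threshold.** The lower limit is p − 1.96·√(p(1−p)/n).
- 136/160 = 85.0%: 0.8500 − 1.96 × 0.02823 = 79.5%, pass.
- 135/160 = 84.4%: 0.84375 − 1.96 × 0.02870 = 78.7%, fail.

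The stated 85% reproduces exactly. It assumes a denominator of 160, which is the planned enrolment. The test as planned uses 160 minus the exclusions.

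**3. Effect of k exclusions on a borderline result.** For each k, take the smallest count that passes on mITT, then count the k subjects as failures.

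| k | mITT result | Lower limit | All enrolled | Lower limit |
|---|---|---|---|---|
| 1 | 135/159 | 79.3%, pass | 135/160 | 78.7%, fail |
| 3 | 133/157 | 79.1%, pass | 133/160 | 77.3%, fail |
| 5 | 132/155 | 79.6%, pass | 132/160 | 76.6%, fail |
| 8 | 129/152 | 79.2%, pass | 129/160 | 74.5%, fail |

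**4. Probability of passing.** Let p be true success among all 160 enrolled and a the share whose device never leaves the microcatheter. The documents give no a, so 1% to 5% is an assumption (1.6 to 8 subjects expected). Then:
- K ~ Bin(160, a) and the mITT size is n = 160 − K.
- Given n, the success count X ~ Bin(n, p/(1−a)).
- c(n) is the smallest count with a lower limit above 79%.
- P(pass) = Σ P(K = k) · P(X ≥ c(160 − k)).

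For example, at p = 79% and a = 5% the rate seen in mITT is 0.79/0.95 = 83.2%.

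| True p, all enrolled | No exclusions | a = 1% | a = 2% | a = 3% | a = 5% |
|---|---|---|---|---|---|
| 79% | 3.5% | 6.3% | 9.9% | 14.9% | 31.2% |
| 85% | 55.4% | 68.5% | 78.4% | 86.6% | 96.7% |
| 90% | 98.3% | 99.5% | 99.9% | >99.9% | >99.9% |

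The column without exclusions is the 136/160 rule.

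**5. What the earlier study implies.** Section 1.3.2 reports: "The device was placed at the neck of the intended target aneurysm and detached in 34/34 cases, a 100% success rate". With 0 failures in 34, the exact two-sided 95% upper limit for the failure rate is 1 − 0.025^(1/34) = 10.3%. That study covered basilar and carotid terminus aneurysms only; this one adds middle cerebral and anterior communicating sites.

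**The case against.** The text and the arithmetic are not in dispute; the case against concerns size and remedy.

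- **The large effects lie at unlikely success rates.** If the failure rate is at most 10.3%, true success is at least 89.7%, and the test passes 97.7% of the time even with no exclusions. True rates of 79% or 85% would produce 34/34 with probability 0.03% (0.79^34) or 0.4% (0.85^34). This stands as a limit on practical effect, except that the earlier study says nothing about the two added locations.
- **The 1% to 5% range is assumed.** At 0.5%, the pass probability at a true 79% is only 4.8%. This also stands. The 31% figure needs both 5% exclusions and a true rate at the goal.
- **mITT was specified openly, and the rule is not inflated against an mITT null.** True, but the endpoint names access as its first element, so the population that matches it includes subjects in whom access failed.
- **The denominator of 160 is not certain.** Sections 3.1 and 5.1.9 speak of 160 evaluable subjects and 160 implants, while the summary and section 4.3 say 160 enrolled. The 135/159 example depends on the last reading; the direction of the bias does not.
- **A procedure-start denominator is wider than the gap, and the source of the 79% goal is not given.** It would also count procedures abandoned before the device was introduced. Access failures at that stage are still access failures, and section 10.1.4 already uses starting the study procedure to identify the subjects it lists. Whether the goal was set for attempted or started procedures cannot be told from the documents.

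**Conclusion.** The concern holds. The planned technical success analysis removes, from numerator and denominator, enrolled subjects who fail the first element of the endpoint, and the error always favours the device.

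Its size cannot be fixed from the documents. It is negligible if the event is as rare as the protocol says or if true success is near 90% or above. It is material only for results near the 85% threshold, where a single exclusion can turn a fail into a pass. The probabilities rest on 160 enrolled and an assumed exclusion share of 1% to 5%.

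Study success is unaffected, because technical success is tested only after both primaries are met. The plan should be changed nonetheless: the reported rate would overstate deliverability whenever such subjects occur, even when the test passes comfortably.

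**What to change.** Test technical success on all enrolled subjects in whom the study procedure was started, counting failure to reach the aneurysm as failure. Section 7.4 already supplies the starting point: "Procedure start time is defined as the point when the guiding catheter is introduced into the subject". State how many enrolled subjects were left out of mITT because the device never left the microcatheter; the disposition summaries in section 10.3.2 do not break this out. The mITT rate can be shown beside the main result.

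As a supportive table only, report events of the primary-safety type in these subjects over their existing 30-day follow-up, combined with the mITT events. Leave the primary safety analysis set as it is.

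The cost is a wording change in sections 10.1.6 and 10.3.5 and one extra table. These subjects are already enrolled, followed for 30 days and covered by the adverse event listing, so no new visits or data are needed. The downside for the sponsor is a slightly lower stated success rate if any such subjects occur.

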4.3. Strategies for Recruitment and Retention

The study will enroll a total of 160 subjects in the United States at up to 28 clinical sites. Once enrolled, each subject will participate in the study for 5 years post-procedure. A recruitment packet, that can be customized, may be provided to each clinical site. The packet may include a sample email/letter to referring physicians, a slide deck explaining the clinical study for presentation at grand rounds or other meeting of referring physicians and a patient information booklet describing the device, the indications, the clinical study and the necessary commitment to completing all study visits.

The Sponsor's intention is for the enrolled subject population to be as representative as possible of the well-defined study population. Investigators will be encouraged to evaluate all unruptured and bifurcation aneurysm patients for participation in the study, and to offer enrollment to all who meet preliminary eligibility criteria.

Clinical sites will be selected for participation in the study based on experience with similar stenting technologies, ample unruptured bifurcation aneurysm patient population, the capacity to screen and enroll a reasonable number of eligible patients, and the ability to perform the required study procedures, per this protocol. Sponsor will attempt to include a diversified group of investigational sites engaging a variety of academic and private institutions geographically located throughout the US. To ensure generalizability of results and minimize the influence of any single site, no more than approximately 20% of the total

enrollment will be allowed at a single site (i.e., a maximum of 32 subjects enrolled per site).

In order to enhance participant retention and compliant follow-up visits, site coordinators will be encouraged to schedule their subject follow-up visits early in the visit windows with ample opportunity to reschedule as needed, before the visit window closes.

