Alternative hypothesis H_A : $p_{\text{Major Stroke/Death}} < 15\%$

Where $p_{\text{Major Stroke/Death}}$ is the rate of Composite of Neurological Death or Major Ipsilateral Stroke (in downstream territory) up to 1 year post-procedure.

Decision Criterion: The decision will be made to reject the null hypotheses and conclude the alternative hypothesis if the upper bound of a two-sided 95% normal approximation based confidence interval is < 15%.

Primary Effectiveness Endpoint Hypotheses:

Null hypothesis H_0 : $p_{\text{CompleteOcclusion}} \leq 46.34\%$

Alternative hypothesis H_A : $p_{\text{CompleteOcclusion}} > 46.3\%$

Where $p_{\text{CompleteOcclusion}}$ is the rate of complete aneurysm occlusion without significant parent artery stenosis ($> 50\%$ stenosis) or prior retreatment at 1 year post-procedure.

Decision Criterion: The decision will be made to reject the null hypotheses and conclude the alternative hypothesis if the lower bound of a two-sided 95% normal approximation based confidence interval is $> 46.3\%$.

Study Success:

The study will be deemed to be a success if the primary safety and effectiveness endpoint null hypotheses are both rejected.

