10.2. Sample Size Justification

Meta-analysis

As described above, a meta-analysis was executed to determine the safety Performance Goals for the proposed NAPA clinical study of the PulseRider using the R package ‘meta^a’ in a [R] environment, version 3.3-2. To obtain an overall proportion from studies reporting a single proportion, a random-effects model was chosen over a fixed-effect model to acknowledge the variations in study design. Additional characteristics of the methodology are:

- Inverse variance method used for weights
- DerSimonian-Laird method used to estimate τ^2
- Logit transformation
- Clopper-Pearson confidence interval for individual studies
- Continuity correction of 0.5 in studies with zero cell frequencies

Based on this meta-analysis, a rate of 9.9% rounded to 10% (95% CI: 5.9% - 16.1%) for death due to neurological causes or major ipsilateral stroke was calculated. A 5% margin of indifference for the primary safety endpoint is proposed, resulting in a PG of 15% for this endpoint. Based on the 1 year results of the ANSWER HDE Study, the anticipated rate for the primary safety endpoint is 7%. Results from a recently published meta-analysis [Fiorella 2017] of wide-neck bifurcation aneurysms indicate that the rate of complete occlusion at 1 year of wide-neck bifurcated aneurysms treated with conventional therapies is 46.3% (95% CI: 39.2% - 53.4%) whereas based on the ANSWER HDE Study the rate of complete occlusion is expected to be 58.8% with the PulseRider device. With Sponsor’s desire to seek superiority to a PG of 46.3% for the primary effectiveness endpoint and an expected attrition rate of 10%, one hundred sixty (160) subjects will provide 80% power for the primary safety endpoint and 85% power for the primary effectiveness endpoint.

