10.3.4. Primary Endpoint Analyses

Primary Safety Endpoint

The primary safety endpoint analysis will be conducted on the mITT analysis set.

If a subject experienced a death due to neurological causes or a major ipsilateral stroke in downstream territory within a year post-procedure then subject will be deemed a failure on the endpoint. If a subject completed the 1 year follow up and did not experience any such event then subject will be deemed a success on the endpoint. If a subject did not complete the 1 year follow up and did not experience such event then the subject will be imputed with a multiple imputation method that will make use of the similarities between the subject's demographic, procedural, and aneurysm characteristics with those of the subjects with a non-missing endpoint (those who either experienced an event and those who completed the study without experiencing an event). The imputation method will also account for the length of time between the procedure and the last time the subject was seen. The longer that time period is, the less likely the subject will be imputed with an event.

Subjects for whom implantation of the PulseRider was attempted but not successful will be followed up to a year. Any safety events which occur due to attempted implant or from retreatment, and which meet the primary safety endpoint definition will count as failures in the analysis. If such a subject is lost to follow-up then subject will be imputed with data based on other subjects for whom the implantation was not successful but who were not lost to follow-up.

The multiple imputation method results in a large collection of imputed datasets. The proportion of primary endpoint events and its variance is computed for each dataset. Within and between imputation variances are then combined according to Rubin's method [Rubin 1996] in order to produce a single variance estimate for the proportion of events.

The endpoint will be considered successful if the upper bound of the 2-sided 95% normal approximation based confidence interval for the rate of events is less than a performance goal of 15%.

Primary Effectiveness Endpoint

The primary effectiveness endpoint analysis will be conducted on the PP analysis set.

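### An access-phase stroke or neurological death that stops the procedure before the device leaves the microcatheter falls outside the 15% safety test, no sensitivity analysis restores it, and follow-up for such subjects is stated inconsistently

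*Combined protocol and SAP*

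**What the plan says.** **Order of events.** Under 7.2.1 a patient is enrolled on the procedure day, after consent, Image Screening Committee approval, the pre-procedure angiogram and confirmation of eligibility. Under 7.4 the procedure starts when the guiding catheter is introduced. Under 10.1.6 treatment counts as attempted, and the subject enters mITT, only when some part of the device has passed the distal end of the microcatheter inside the subject.

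**Analysis.** Section 10.3.4 runs the primary safety endpoint on mITT. Section 10.1.1 rejects the null hypothesis "if the upper bound of a two-sided 95% normal approximation based confidence interval is < 15" percent. For a subject who started the procedure but "did not undergo attempted treatment with the study device and therefore is not part of the modified Intent To Treat (mITT) population", section 10.1.4 provides a listing of adverse events. The sensitivity analyses in 10.3.10 all concern missing endpoint data.

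**Follow-up.** The relevant statements are:
- 4.3: "Once enrolled, each subject will participate in the study for 5 years post-procedure".
- Table 7.15A, footnote: subjects without an implant are excused the 1-year DSA. Nothing else is waived.
- 10.1.6, where the device does not reach the aneurysm and so is not advanced: "the subject will not be considered part of the mITT population and will instead be followed for 30 days".
- 10.3.4: "Subjects for whom implantation of the PulseRider was attempted but not successful will be followed up to a year".

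**The concern.** Whether a subject belongs to the primary safety set is decided during the procedure, after exposure to its risks has begun. Between introduction of the guiding catheter and passage of the device beyond the microcatheter tip, an enrolled subject can have a perforation or a thromboembolic stroke. If that event is why the operator stops, the outcome itself removes the subject from both numerator and denominator of the 15% test.

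The provision in 10.3.4 for attempted but unsuccessful implants does not bring the subject back, because attempted carries the 10.1.6 definition. At stake is an outcome-dependent exclusion from a primary endpoint, with no planned analysis to show whether it mattered.

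The follow-up statements add a practical problem. The endpoint runs to 1 year, and sites reading different sections could stop collecting data on these subjects at different times.

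**Working it through.** **1. The plan's own figure.** Section 10.2 states that "the anticipated rate for the primary safety endpoint is 7" percent and that, with "an expected attrition rate of 10%, one hundred sixty (160) subjects will provide 80% power for the primary safety endpoint". The level is set in 10.1.5: "A 2-sided alpha of 0.05 will be used for statistical testing and confidence intervals unless otherwise noted". Inputs: n = 160 × 0.9 = 144, expected rate 0.07, goal 0.15, z = 1.96. With null variance and a continuity correction of 1/(2n):

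power = Φ{[0.15 − 0.07 − 1/288 − 1.96 × √(0.15 × 0.85/144)] / √(0.07 × 0.93/144)}
= Φ{[0.08 − 0.00347 − 1.96 × 0.02976] / 0.02126} = Φ(0.856) = 80.4%.

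The stated 80% reproduces and is not in dispute.

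**2. The decision limit.** Upper bound = p + 1.96 × √(p(1 − p)/n), with p = events/n, ignoring multiple imputation.

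| Counted | Working | Upper bound | Result |
|---|---|---|---|
| 16/160 | 0.1000 + 1.96 × 0.02372 | 14.65% | pass |
| 17/160 | 0.10625 + 1.96 × 0.02436 | 15.40% | fail |
| 16/159 | 0.10063 + 1.96 × 0.02386 | 14.74% | pass |
| 14/143 | 0.09790 + 1.96 × 0.02485 | 14.66% | pass |
| 15/144 | 0.10417 + 1.96 × 0.02546 | 15.41% | fail |

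One excluded subject with an endpoint event is the difference between 17/160 (fail) and 16/159 (pass), or between 15/144 (fail) and 14/143 (pass).

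**3. How often one such event would decide the result.** Suppose exactly one of 160 subjects is excluded and that subject had an event. The verdict changes only if the other 159 have exactly 16 events. The binomial probability of that is 3.8% at a true mITT rate of 7%, and 10.5% at 10%.

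**4. Effect on the error rate.** Suppose the true rate among all 160 is exactly 15%. The documents give neither the share excluded (f) nor the event rate among those excluded (q), so both are assumptions. The mITT rate is then (0.15 − f·q)/(1 − f). The chance of declaring success is the binomial probability of no more than the largest passing count.

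| f | q | mITT n | mITT rate | Largest passing count | Chance of success |
|---|---|---|---|---|---|
| 0 | – | 160 | 15.0% | 16 | 4.3% |
| 2% | 15% | 157 | 15.0% | 16 | 5.2% |
| 2% | 50% | 157 | 14.3% | 16 | 8.4% |
| 5% | 15% | 152 | 15.0% | 15 | 4.3% |
| 5% | 50% | 152 | 13.2% | 15 | 13.9% |
| 5% | 100% | 152 | 10.5% | 15 | 46% (extreme) |

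The 4.3% in the first row belongs to the normal-approximation rule and is the baseline here. When excluded subjects share the common 15% rate, the chance stays close to it (3.5% to 5.2% for f from 1% to 5%). The rise comes only from a higher event rate among those excluded.

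**5. Follow-up, side by side.**

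| Enrolled subject | Stated follow-up |
|---|---|
| Any | 5 years (4.3) |
| Not implanted | Schedule applies, 1-year DSA waived (Table 7.15A) |
| Attempted, not successful (in mITT) | Up to a year (10.3.4) |
| Device does not reach the aneurysm (outside mITT) | 30 days (10.1.6) |
| Procedure stopped by a complication before deployment (outside mITT) | None expressly stated |

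**The case against.** The case for leaving the plan alone has real force on several points.

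- **The 30-day sentence is narrower than it first looks.** A reader might infer that a subject whose procedure is stopped by a stroke is followed for only 30 days. The text does not say so. That sentence concerns a device that fails to reach the aneurysm. A complication-driven stop is excluded by the mITT definition, and its follow-up is simply not stated.
- **The event is not hidden, and 30 days would not miss it.** Adverse events are collected from enrolment (8.3), neurological and serious events are reportable (8.1.1), the Clinical Events Committee reviews all reportable events (8.5), and 10.1.4 lists them. An event that causes abandonment happens during the procedure. The shorter follow-up loses only later events.
- **10.1.6 and 10.3.4 do not contradict each other on duration.** They describe different groups. The tension is between 10.1.6 on one side and 4.3 and Table 7.15A on the other. One can read 10.1.6 as a specific exception to a general statement, but the plan does not say that it is.
- **The size may be very small.** The plan calls the situation rare, and 1.3.2 reports 34 of 34 placements in the earlier study. That is limited reassurance: the exact two-sided 95% upper bound for 0/34 failures is 1 − 0.025^(1/34) = 10.3%, and that study did not include MCA or ACOM aneurysms.
- **A device-attempted set is a legitimate choice.** The threshold is objective, and failed attempts beyond it are counted. The documents do not show whether the series behind the 15% goal counted access-phase events, so neither denominator is shown to match the goal better.

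These points remove any case for calling the primary set wrong. They do not answer the remaining gap: no pre-specified analysis applies the 15% test with these subjects included. Section 10 says a separate, more detailed SAP will follow; it is not in the file, so whether it closes the gap cannot be checked.

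**Conclusion.** The point holds in limited form. The mITT definition permits exclusion from the primary safety test because of the outcome, and none of the analyses listed in 10.3.10 would reveal its effect. A reader might go further and conclude that the safety rate is biased downward. That follows only if excluded subjects have a higher event rate than mITT subjects. This is plausible when a complication stopped the procedure, but the documents do not show it.

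One excluded event reverses the result only at the limit (16/159 against 17/160). At the plan's expected 7%, about 11 of 160, that would happen in roughly 4% of cases in which one such event occurred. The larger error rates rest on assumed exclusions of 2% to 5% with half or more having events.

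Separately, the follow-up statements for enrolled subjects outside mITT do not agree, and one group has no stated duration. Both matters are worth correcting because the correction is cheap and data not collected cannot be recovered later. Neither invalidates the design.

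**What to change.** 1. Keep mITT as the primary safety set if preferred. In 10.3.10, pre-specify the 15% test as a sensitivity analysis on all enrolled subjects whose index procedure was started as defined in 7.4 (guiding catheter introduced), counting their endpoint events as adjudicated by the Clinical Events Committee.
2. For subjects in that set but outside mITT, seek endpoint status to 1 year, without study DSA, so that the analysis covers the same period as the endpoint.
3. Reconcile 4.3, Table 7.15A and 10.1.6 so that one follow-up duration is stated for each group, including subjects whose procedure is stopped by a complication before deployment.

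Cost: a protocol and SAP wording change, and clinical follow-up contact for what should be a few more subjects. The sensitivity result may be slightly less favourable than the mITT result.
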